## **9.2 Efficacy Analysis by Week 12**

### **9.2.1 Primary Efficacy Analysis**

The primary endpoint for US/FDA regulatory purposes is ACR20 response at Week 12. The primary endpoint for EU/EMA regulatory purposes is LDA (based on DAS28 (CRP)  $\leq 3.2$ ) at Week 12. Analyses will be conducted separately for US/FDA regulatory purposes and EU/EMA regulatory purposes; for each set of analysis, only one primary endpoint is specified.

Analysis of the primary endpoint will be conducted on the FAS based on randomized treatment groups (Upadacitinib 15 mg QD, Upadacitinib 30 mg QD and the combined placebo groups). Point estimate and 95% CI using normal approximation will be

provided for the response rate for each randomized treatment group. Comparisons of the primary endpoint will be made between each Upadacitinib dose and the combined placebo group using the Cochran-Mantel-Haenszel test adjusting for stratification factor prior bMDARD use. Point estimate, 95% CI using normal approximation and p-value for the treatment comparison will be presented. Both the nominal p-value constructed using the Cochran-Mantel-Haenszel test and the adjusted p-value through the graphical multiplicity procedure described in Section 9.2.5 will be provided. For the primary analysis, non-responder imputation (NRI) will be used.

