###### **8.1.4.1.1 Primary Efficacy Variable**

The primary endpoint (at Week 12) for US/FDA regulatory purposes is listed in Section 5.3.3.1.1. The primary endpoint (at Week 12) for EU/EMA regulatory purposes is also listed in Section 5.3.3.1.1. Analyses will be conducted separately for US/FDA regulatory purposes and EU/EMA regulatory purposes; for each set of analysis, only one primary endpoint is specified.

Analysis of the primary endpoint will be conducted on the FAS based on treatment as randomized. Comparisons of the primary endpoint will be made between each upadacitinib dose and the combined placebo group using the Cochran-Mantel-Haenszel test adjusting for main stratification factors. For the primary analysis, non-responder

imputation (NRI) will be used. The analysis will be repeated using Observed Cases (OC). Supportive analysis will also be conducted on the Per Protocol Analysis Set.

The primary efficacy analyses will be performed in demographic subgroups including age, gender, weight, body mass index, race, and geographical region to assess the consistency of the treatment effect. Additional subgroup analyses based on baseline disease characteristics and stratification factors will also be conducted.

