#### **8.1.4.1.2 Key Secondary Efficacy Variables**

Key secondary endpoints (at Week 12): Key secondary endpoints (at Week 12) for US/FDA regulatory purposes are listed in Section 5.3.3.1.2. Key secondary endpoints (at Week 12) for EU/EMA regulatory purposes are also listed in Section 5.3.3.1.2.

For binary endpoints, frequencies and percentages will be reported for each treatment group. Similar analyses as for the primary endpoint will be conducted.

For continuous endpoints, the mean, standard deviation, median, and range will be reported for each treatment group. Between-group comparisons for each upadacitinib treatment group and the combined placebo groups will be performed using the analysis of covariance model with treatment as the fixed factor, and the corresponding baseline value and the main stratification factors as the covariates.

See Section 8.1.4.1.5 for imputation methods.

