### **8.3 Randomization Methods**

Subjects will be randomly assigned in a 2:2:1:1 ratio to one of the four treatment groups:

- Group 1: upadacitinib 30 mg QD, N = 150 (Day 1 to Week 12) → upadacitinib 30 mg QD (Week 12 and thereafter)
- Group 2: upadacitinib 15 mg QD, N = 150 (Day 1 to Week 12) → upadacitinib 15 mg QD (Week 12 and thereafter)
- Group 3: Placebo, N = 75 (Day 1 to Week 12) → upadacitinib 30 mg QD (Week 12 and thereafter)
- Group 4: Placebo, N = 75 (Day 1 to Week 12) → upadacitinib 15 mg QD (Week 12 and thereafter)

Randomization will be stratified by number of prior bDMARD use (stratum 1: failed 1 or 2 biologics with the same mechanism of action; stratum 2: failed  $\geq 3$  biologics with the same mechanism of action and/or multiple mechanisms of action) and geographic region. Once approximately 35% of the total subjects have been randomized in stratum 2, further screening of subjects who meet stratum 2 criteria may be suspended.

See Section 5.5.3 for details.

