#### **4.2 Overall Study Design and Plan**

This is a Phase 3, multicenter study that includes two periods. Period 1 is the 24-week randomized, double-blind, parallel-group, placebo-controlled period designed to compare the safety and efficacy of Upadacitinib 30 mg QD and 15 mg QD versus placebo for the treatment of signs and symptoms of subjects with moderately to severely active RA who have an inadequate response to or intolerance to bDMARD therapy and are currently on a stable dose of csDMARDs. Period 2 is a blinded long-term extension to evaluate the

long-term safety, tolerability, and efficacy of Upadacitinib 30 mg QD and 15 mg QD in subjects with RA who have completed Period 1. Starting with Amendment 4, all subjects will receive open-label upadacitinib 15 mg QD, including those currently on upadacitinib 30 mg QD.

The study is designed to enroll approximately 450 subjects at approximately 350 study centers worldwide to meet scientific and regulatory objectives without enrolling an undue number of subjects in alignment with ethical considerations. Therefore, if the target number of subjects has been enrolled, there is a possibility that additional subjects in screening may not be enrolled.

The study duration includes a 35-day screening period; a 24-week randomized, double-blind, parallel-group, placebo controlled treatment period (Period 1); a 236-week blinded extension period (Period 2); and a 30-day follow-up (call or site visit).

Subjects who meet eligibility criteria will be randomized in a 2:2:1:1 ratio to one of four treatment groups:

- Group 1: Upadacitinib 30 mg QD, N = 150 (Day 1 to Week 12) → Upadacitinib 30 mg QD (Week 12 and thereafter)
- Group 2: Upadacitinib 15 mg QD, N = 150 (Day 1 to Week 12) → Upadacitinib 15 mg QD (Week 12 and thereafter)
- Group 3: Placebo, N = 75 (Day 1 to Week 12) → Upadacitinib 30 mg QD (Week 12 and thereafter)
- Group 4: Placebo, N = 75 (Day 1 to Week 12) → Upadacitinib 15 mg QD (Week 12 and thereafter)

Randomization is stratified by number of prior bDMARD (stratum 1: failed 1 or 2 biologics with the same mechanism of action; stratum 2: failed  $\geq 3$  biologics with the same mechanism of action and/or multiple mechanisms of action) and geographic region.

Subjects must have been receiving csDMARD therapy  $\geq 3$  months and have been on a stable dose of csDMARD(s) for  $\geq 4$  weeks prior to the first dose of study drug and must

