### **Mixed Effect Model Repeat Measurement (MMRM) for Short-Term Analysis**

The repeated measure analysis will be conducted using mixed model including observed measurements at all visits. The mixed model includes the categorical fixed effects of treatment, visit and treatment-by-visit interaction, main stratification factors at randomization and the continuous fixed covariates of baseline measurement. An unstructured variance covariance matrix will be used. The parameter estimations are based on the assumption of data being missing at random and using the method of restrictive maximum likelihood (REML). The missing at random assumption is considered reasonable given the high placebo response rate typically seen in RA trials. Additionally in RA trials, the proportion of discontinuation is relatively small (10 – 15% only) and the rate of discontinuation due to lack of efficacy is generally low (< 5%).

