### **MMRM and Generalized Linear Mixed Model (GLMM) for Long-Term Analysis**

The repeated measure analysis will be conducted using mixed model including As Observed measurements at all visits. MMRM will be used for continuous endpoints and GLMM will be used for binary endpoints. The mixed models will include the categorical fixed effects of treatment, visit and treatment-by-visit interaction, and main stratification factor prior bDMARD use. For the MMRM analysis of change from baseline in continuous endpoints, the baseline measurement will be included as a continuous fixed covariate. The categorical fixed effect of subject's discontinuation status may also be

included in the model as appropriate. Unstructured, Toeplitz, compound symmetry, or other covariance structures may be considered.

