### **9.2.3 Key Secondary Efficacy Analyses**

Ranked key secondary endpoints (at Week 12) for US/FDA regulatory purposes are:

1. Change from baseline in DAS28 (CRP);
2. Change from baseline in HAQ-DI;
3. LDA as measured by DAS28 (CRP);
4. Change from baseline in SF-36 Physical Component Score (PCS).

Ranked key secondary endpoints (at Week 12) for EU/EMA regulatory purposes are:

1. Change from baseline in DAS28 (CRP);
2. ACR20 response rate;
3. Change from baseline in HAQ-DI;

4. Change from baseline in SF-36 Physical Component Score (PCS).

Other key secondary endpoints (at Week 12) for both US/FDA and EU/EMA regulatory purposes are:

1. ACR50 response rate;
2. ACR70 response rate;
3. ACR20 response rate at Week 1.

For binary endpoints, frequencies and percentages will be reported for each randomized treatment group. Similar analyses as for the primary endpoint will be conducted.

For the major RA continuous endpoints DAS28 and HAQ-DI change from baseline, statistical inference will be conducted using analysis of covariance (ANCOVA) coupled with MI for missing data handling. Specifically, the ANCOVA model will include treatment as the fixed factor, and the corresponding baseline value and the stratification factor prior bDMARD use (Yes/No) as the covariates. For other continuous endpoints, statistical inference will be conducted using the MMRM model as described in Section 9.1.2, with the main stratification factor being prior bDMARD use (Yes/No). From both the MI and MMRM analyses, the LS mean and 95% CI will be reported for each randomized treatment group; the LS mean treatment difference and associated 95% CI and p-value will be reported comparing each Upadacitinib dose group with the combined placebo group. Both nominal p-value and adjusted p-value through the graphical multiplicity procedure described in Section 9.2.5 will be provided.

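### Region is a randomisation stratum, but the SAP, without explanation, names only prior bDMARD use in its efficacy models; if region is prognostic, the Week 12 tests are somewhat conservative and give up a little precision

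*SAP*

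**What the plan says.** **Randomisation.** Protocol 5.3.1.1, 5.5.3 and 8.3 and SAP 4.2 give two stratification factors. One is prior failed bDMARD (stratum 1 or stratum 2), the other is region: "multiple mechanisms of action) and geographic region" (protocol 8.3).

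**Protocol analysis.** The primary test is a "Cochran-Mantel-Haenszel test adjusting for main stratification factors" (8.1.4.1.1). The ANCOVA takes the baseline value and the "main stratification factors as the covariates" (8.1.4.1.2). Neither section names the factors, and protocol 8.1 leaves specific details to the SAP.

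**SAP analysis.**
- Primary test (9.2.1): a "Cochran-Mantel-Haenszel test adjusting for stratification factor prior bMDARD use". Binary key secondary and exploratory endpoints follow the same pattern (9.2.3, 9.2.4, Table 4).
- ANCOVA for DAS28 and HAQ-DI (9.2.3): baseline value and prior bDMARD use, coded Yes/No.
- Week 12 MMRM for other continuous endpoints (9.2.3): "with the main stratification factor being prior bDMARD use (Yes/No".
- Short-term MMRM as defined in 9.1.2: "main stratification factors at randomization and the continuous fixed covariates of baseline measurement". Here the plural returns and no factor is named.
- Long-term MMRM and GLMM (9.1.2): "main stratification factor prior bDMARD use".
- Multiple imputation (9.1.2): the regression includes demographic and baseline variables that are not listed individually.

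Otherwise region appears as a baseline characteristic (6.1) and a subgroup for the primary endpoint (Table 3).

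**The concern.** Stratified randomisation balances the arms within region. If response differs between regions, that balance removes variation from the treatment comparison. An analysis that ignores region still counts the variation as error, so its standard error is too large, its test rejects too seldom under the null, and the precision that the stratification could have delivered is not used.

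The plan's wording also does not settle which factors are meant. The protocol uses a plural where only two factors exist. The SAP uses the plural in one place and a single factor everywhere else. The Yes/No coding in 9.2.3 does not describe the randomisation stratum at all. A programmer could not tell from this text whether region was left out on purpose.

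**Working it through.** **1. The plan's own power figure.** Inputs from protocol 8.2 and SAP 4.3: total 450, so 150 per arm with the placebo groups pooled; 10% dropout, so 135; two-sided alpha 0.025, so z = 2.2414; ACR20 27% v 47%; LDA 12% v 29%. With p̄ the mean of the two rates:

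power = Φ{ [Δ√n − z√(2p̄(1−p̄))] / √(p₀(1−p₀) + p₁(1−p₁)) }

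- ACR20: [0.20 × 11.619 − 2.2414 × √0.4662] / √0.4462 = 1.188, power 88.3%.
- LDA: [0.17 × 11.619 − 2.2414 × √0.32595] / √0.3115 = 1.246, power 89.4%.

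Both agree with the stated figure of about 90%. The formula has no stratification term, so the stated power does not depend on how region is handled.

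**2. Effect of leaving region out.** The documents give no regional response rates, so this step rests on assumptions. Trials of 450 subjects were simulated with permuted blocks within 6 regions × 2 bDMARD strata, 6,000 trials per scenario, no dropout. SAP 6.1 lists six regions; the number used in the IRT is not stated. Assumed: region shares 25/15/20/25/10/5%, stratum 2 share 35% (the cap in protocol 8.3), log-odds effect of stratum 2 of −0.4, and overall rates held at the protocol values. Each data set was tested twice with

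z = Σₖ(aₖ − n₁ₖm₁ₖ/nₖ) / √Σₖ[n₁ₖn₀ₖm₁ₖm₀ₖ / (nₖ²(nₖ−1))],

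where, in stratum k, aₖ is the number of responders on active drug, n₁ₖ and n₀ₖ are the arm sizes, m₁ₖ and m₀ₖ are the numbers of responders and non-responders, and nₖ is the total. The strata were first prior bDMARD only (2), then bDMARD × region (12). A trial rejects when |z| > 2.241. In the tables, arrows run from without region to with region, and gains come from unrounded figures.

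ACR20:

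| SD of region log-odds | Placebo rate by region | Type I error, % | Power, % | Gain, points |
|---|---|---|---|---|
| 0 | 27% | 2.4 → 2.4 | 91.9 → 91.9 | 0.0 |
| 0.25 | 22–34% | 2.2 → 2.3 | 91.9 → 92.1 | 0.2 |
| 0.5 | 17–42% | 2.1 → 2.5 | 92.3 → 93.0 | 0.7 |
| 0.75 | 13–50% | 1.8 → 2.5 | 92.9 → 94.7 | 1.8 |
| 1.0 | 9–56% | 1.2 → 2.4 | 93.3 → 96.0 | 2.7 |

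LDA:

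| SD of region log-odds | Placebo rate by region | Type I error, % | Power, % | Gain, points |
|---|---|---|---|---|
| 0 | 12% | 2.4 → 2.5 | 92.8 → 92.7 | −0.1 |
| 0.25 | 9–16% | 2.7 → 2.7 | 93.1 → 93.1 | 0.0 |
| 0.5 | 7–21% | 2.1 → 2.3 | 93.1 → 93.5 | 0.5 |
| 0.75 | 5–25% | 1.9 → 2.3 | 94.2 → 95.3 | 1.1 |
| 1.0 | 3–29% | 2.0 → 2.7 | 94.6 → 96.4 | 1.9 |

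The Monte Carlo standard error is about 0.2 points for type I error and 0.35 for a single power figure. The two tests use the same simulated trials. No type I error exceeds 2.5% by more than simulation error.

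**3. The Yes/No coding.** Inclusion criterion 3 (protocol 5.2.1) requires every subject to have had bDMARD therapy. A Yes/No indicator of prior use is therefore constant. Read literally, the ANCOVA and the SF-36 PCS MMRM in SAP 9.2.3 would adjust for neither randomisation factor. The intended covariate is presumably the stratum 1/stratum 2 factor in SAP 4.2 and 6.1.

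**The case against.** **A reader might infer that the SAP contradicts the protocol.** The documents do not support that. The protocol never defines 'main' and hands the details to the SAP, which names one main factor. The plural reads most naturally as both factors, but what can be shown is an unexplained narrowing.

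**A reader might infer that no efficacy analysis accounts for region.** That is also too strong. The short-term MMRM definition in 9.1.2 could cover region. So could the imputation model, since SAP 6.1 lists region among the main demographic and baseline characteristics.

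**There may be a good reason to leave region out.** Six regions by two strata make 12 cells, on average 300/12 = 25 subjects each in a pairwise comparison. Under the assumed shares, the smallest cell expects 300 × 0.05 × 0.35 ≈ 5. Adjusting for a subset of factors to avoid sparse cells is defensible, so the omission cannot be called pointless. But the SAP does not give this reason, and with 12 cells and no region effect the simulated cost was only 0.0 (ACR20) and 0.1 (LDA) power points.

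**The Week 12 analysis is finished.** SAP 11.1 says that it was completed under version 2.0, Appendix B dates completion to 2017, and section 12.0 records that version 2.0 incorporated FDA feedback. This stands: the confirmatory test cannot be re-specified now.

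**The long-term analysis has no hypothesis tests** (SAP 9.1.1). This also stands. Alpha and power are not at issue there, only the precision of model estimates, and that was not quantified.

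**Conclusion.** The point holds as an unexplained narrowing with a modest, conditional cost. The loss depends on region being prognostic, and the documents give no figure for that. On the assumed rates, it is at most 0.7 power points up to a log-odds SD of 0.5, 1.1–1.8 points at 0.75, and 1.9–2.7 points at 1.0, where placebo ACR20 would have to range from 9% to 56%.

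Two further inferences should be resisted. One is that planned power has been eroded. Without region, simulated power stays at 91.9–93.3% for ACR20 and 92.8–94.6% for LDA across all scenarios, so what is lost is a possible gain. The other is that every ranked test is known to run below its alpha. Only ACR20 and LDA were simulated. The continuous endpoints were not, and their baseline adjustment may absorb part of any regional difference.

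The error is in the conservative direction, so it casts no doubt on a positive Week 12 result. The Yes/No coding needs correcting whatever is decided about region.

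**What to change.** - **Long-term models (SAP 9.1.2, 9.3).** Add region as a fixed effect in the MMRM and GLMM, or state why not. SAP 3.0 still governs this reporting.
- **Week 12.** Report a region-adjusted sensitivity analysis of the primary and ranked endpoints: CMH strata of prior bDMARD stratum × region, and region added to the ANCOVA and MMRM. Label it post hoc. Pool small regions by size alone, never by response. Leave the completed primary analysis as it is, and state why region was omitted from it.
- **Wording.** Make the short-term and long-term model definitions in 9.1.2 agree with 9.2.1 and 9.2.3, naming the factors each time. Replace the Yes/No coding with the stratum 1/stratum 2 factor. State whether region is in the imputation model.

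The cost is SAP wording, a few extra model runs, and one covariate already held as a randomisation stratum. The small downside is that a few sparse cells contribute little information.

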### **9.2.2 Sensitivity Analysis of Primary Efficacy Variables**

The primary analysis for point estimate and CI will be repeated using Observed Cases without any imputation as a sensitivity analysis. This will be conducted on the FAS based on randomized treatment groups.

Supportive NRI analysis will also be conducted on the Per Protocol Analysis Set.

### **9.2.3 Key Secondary Efficacy Analyses**

Ranked key secondary endpoints (at Week 12) for US/FDA regulatory purposes are:

1. Change from baseline in DAS28 (CRP);
2. Change from baseline in HAQ-DI;
3. LDA as measured by DAS28 (CRP);
4. Change from baseline in SF-36 Physical Component Score (PCS).

Ranked key secondary endpoints (at Week 12) for EU/EMA regulatory purposes are:

1. Change from baseline in DAS28 (CRP);
2. ACR20 response rate;
3. Change from baseline in HAQ-DI;

4. Change from baseline in SF-36 Physical Component Score (PCS).

Other key secondary endpoints (at Week 12) for both US/FDA and EU/EMA regulatory purposes are:

1. ACR50 response rate;
2. ACR70 response rate;
3. ACR20 response rate at Week 1.

For binary endpoints, frequencies and percentages will be reported for each randomized treatment group. Similar analyses as for the primary endpoint will be conducted.

For the major RA continuous endpoints DAS28 and HAQ-DI change from baseline, statistical inference will be conducted using analysis of covariance (ANCOVA) coupled with MI for missing data handling. Specifically, the ANCOVA model will include treatment as the fixed factor, and the corresponding baseline value and the stratification factor prior bDMARD use (Yes/No) as the covariates. For other continuous endpoints, statistical inference will be conducted using the MMRM model as described in Section 9.1.2, with the main stratification factor being prior bDMARD use (Yes/No). From both the MI and MMRM analyses, the LS mean and 95% CI will be reported for each randomized treatment group; the LS mean treatment difference and associated 95% CI and p-value will be reported comparing each Upadacitinib dose group with the combined placebo group. Both nominal p-value and adjusted p-value through the graphical multiplicity procedure described in Section 9.2.5 will be provided.

#### **9.2.4 Exploratory Efficacy Analyses**

Additional efficacy analysis includes the following endpoints at Week 1, 2, 4, 8 and 12:

- Change from baseline in individual components of ACR response;
- ACR20/50/70 response rates;

- Change from baseline in DAS28 (CRP) and DAS28 (erythrocyte sedimentation rate [ESR]);
- Change from baseline in CDAI and SDAI;
- Change from baseline in morning stiffness (severity and duration);
- Proportion of subjects achieving LDA and proportion of subjects achieving CR based on DAS28 (CRP), DAS28 (ESR), Simplified Disease Activity Index (SDAI), and CDAI criteria;
- Proportion of subjects achieving MCID in change from baseline in HAQ-DI (defined as change from baseline in HAQ-DI  $\leq -0.3$ ) among those with baseline HAQ-DI  $\geq 0.3$ ;
- ACR/EULAR Boolean remission.

Additional endpoints (at Weeks 4 and 12) are:

- Change from baseline in EQ-5D-5L;
- Change from baseline in ISI (sleep);
- Change from baseline in SF-36.

For binary endpoints, point estimate and 95% CI using normal approximation will be provided for the response rate for each randomized treatment group. Point estimate, 95% CI and p-value will be provided for the treatment comparison between each Upadacitinib dose group and the combined placebo group using the Cochran-Mantel-Haenszel test adjusting for stratification factor prior bDMARD use. Only the nominal p-value will be provided, and the 95% CI will be based on normal approximation. NRI will be used as primary analysis and OC will be used as sensitivity analysis.

For continuous endpoints, the LS mean and 95% CI will be reported for each randomized treatment group. The LS mean treatment difference and associated 95% CI and p-values between each Upadacitinib dose group and the combined placebo group will be provided using MMRM model with fixed effects of treatment, visit and treatment-by-visit interaction, prior bDMARD use and baseline value as covariate. Only the nominal p-value will be provided.

[figure not shown]
### 9.2.5 Handling of Multiplicity

The overall type I error rate of the primary and ranked key secondary endpoints for the two doses will be strongly controlled using a graphical multiple testing procedure. Specifically, the testing will utilize the endpoint sequence of primary endpoint followed by the ranked key secondary endpoints in the order as specified in Section 9.2.3, and will begin with testing the primary endpoint using  $\alpha$  of 0.025 for each dose. Continued testing will follow a pre-specified  $\alpha$  transfer path which includes downstream transfer along the endpoint sequence within each dose as well as cross-dose transfer. Adjusted p-values for the primary and ranked key secondary endpoints will be provided based on the testing procedure.

[figure not shown]
The graphs for the testing procedures are provided in Figure 3 and Figure 4, for US/FDA and EU/EMA regulatory purposes respectively. In the graph, the arrows specify the  $\alpha$  transfer paths. Once an endpoint is rejected (i.e., deemed significant) at its assigned significance level, its significance level will be transferred to subsequent endpoint(s) following the arrow(s). The numbers on the arrows denote the weights for transferring significance levels. Specifically, the weight 1 denotes 100% transfer of significance level.

